8.2 Blinding

The order in which participants complete the two treatment phases (i.e., oral methamphetamine and placebo) will be unknown to both the participants and the PI/study team. Both the oral methamphetamine and placebo will be prepared in identical capsules by the UCSF CTSI investigational pharmacist, out of sight of the study participant, study coordinator, and study site PI and administered to the participant to maintain double blinding. The investigational pharmacist will randomize each participant according to the methods described above. In the event that participant experiences an adverse event that requires the identity of the study drug be revealed, the PI will be able to contact the investigational pharmacist to break the blind. In the event that a participant blind is broken, the study PIs will determine the impact upon the un-blinded participant's continued participation in the study and if a replacement participant is needed on a case-by-case basis.

8.3 Formulation of Test and Control Products

8.3.1 Formulation of Test Product

Oral methamphetamine hydrochloride (10 mg, then 15 mg) will be administered in a double-blind fashion and prepared by over-encapsulating commercially available drug with cornstarch; placebo capsules will contain only cornstarch. Study drug will be labeled and stored at <30° Celsius and protected from light. The half-life of oral MA is 4-5 hours, with 62% of drug eliminated in the urine within the first 24 hours, (1/3 as intact drug and the remainder as metabolites).⁶⁰ Individuals with chronic, tolerant MA use are reported to take between 250-500 mg and 1000 mg of MA per episode of use.²¹ Since participants included in this study will have no prior or recent MA use, they will be considered to be non-tolerant. Thus, given prior data demonstrating physiologic effects⁶¹⁻⁶³ at doses similar to what is proposed here (maximum of 25 mg oral per day as recommended for the treatment of attention deficit hyperactivity disorder in children⁶⁰), an initial 10 mg will be administered to assess tolerability, followed by a subsequent 15 mg dose two hours later.

8.3.2 Formulation of Control Product

As above; capsules will contain cornstarchonly.

8.4 Supply of Study Drug at the Site

8.4.1 Dosage/Dosage Regimen

An initial 10 mg of oral methamphetamine study drug will be administered to assess tolerability, followed by a subsequent 15 mg oral dose two hours later. For placebo treatment phase, one placebo capsule will be administered orally on treatment day, followed by a second oral placebo capsule two hours later.

8.4.2 Dispensing

All handling of the study drug and placebo - storage, reconstitution, individual dose preparation, and drug accountability will be done by the study investigators and the investigational pharmacist.

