4 STUDY DESIGN

4.1 Study Overview

This is a phase IV open label randomized, double-blinded, placebo-controlled crossover study. A placebo treatment arm will be assigned to participants in a randomized crossover design. HIV+ ART-suppressed individuals with no prior history of MA use disorder will be administered 10mg oral methamphetamine hydrochloride (Desoxyn®), followed by 15 mg methamphetamine hydrochloride two hours later, for a total of 25mg in one 24-hour period (the maximum FDA approved daily dose for the treatment of childhood obesity). Participants will complete the study twice (once on a placebo treatment arm and once with the Desoxyn® treatment arm). Which treatment arm occurs first will be randomly assigned and will include a 31-day washout period between the two phases. The placebo is similar in appearance, consistency, and taste to methamphetamine hydrochloride tablets, USP (Desoxyn®), without any known drug-drug interactions (e.g., changes in pH balance that might affect drug absorption) with HIV antiretroviral therapy.

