8.6 Study Drug Accountability

An accurate and current accounting of the dispensing of study drug for each participant will be maintained on an ongoing basis by the study investigators. The number of study drug dispensed will be recorded on the Investigational Drug Accountability Record. The study investigators will verify these documents throughout the course of the study.

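### Section 8.4.2 has the study investigators share in individual dose preparation and drug accountability, contradicting 8.2 and 8.5.1; followed as written, it would unblind any investigator who prepares a dose.

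*Combined protocol and SAP*

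**What the plan says.** Section 8.2 (Blinding) states that the order of the two treatment phases "will be unknown to both the participants and the PI/study team". Both products are to be "prepared in identical capsules by the UCSF CTSI investigational pharmacist, out of sight of the study participant, study coordinator, and study site PI". The same section adds: "The investigational pharmacist will randomize each participant according to the methods described above". If an adverse event requires the treatment to be revealed, "the PI will be able to contact the investigational pharmacist to break the blind".

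Section 8.4.2 (Dispensing) covers all handling of drug and placebo, from storage onward, and says that "individual dose preparation, and drug accountability will be done by the study investigators and the investigational pharmacist".

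Section 8.5.1 (Storage) keeps both products in a locked cabinet in the investigational pharmacy. Entry is by electronic pass key and restricted to pharmacy and housekeeping staff. The investigational pharmacist dispenses and keeps the distribution records.

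Section 8.6 (Study Drug Accountability) says that the accounting of what is dispensed to each participant "will be maintained on an ongoing basis by the study investigators". The investigators also verify these records during the study.

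Section 4.1 describes the trial in these words: "This is a phase IV open label randomized, double-blinded, placebo-controlled crossover study". The study design row of the synopsis likewise uses both labels.

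**The concern.** Under 8.2 the pharmacist is the one person who knows the assignment, and the PI has to ask the pharmacist for it. Section 8.4.2 gives the investigators a share in the step at which the assignment is visible. By 8.3.1 the active capsule holds over-encapsulated drug and the placebo capsule holds cornstarch alone, so whoever fills or makes up a dose knows which it is.

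The blind matters here because several safety and retention decisions rest on investigator judgement:

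- The PI is the primary medical monitor for adverse events (10.3), and the team assesses relatedness (13).
- Relatedness feeds the pausing rule in 10.4 and, for Grade 3 events, the enrolment hold in 13.
- The PI decides on further drug administration (10.4) and on withdrawal after a protocol violation (12). An investigator may discontinue a participant on judgement (11.1).
- A participant who withdraws before the last dosing day is replaced (12.4), so a withdrawal decision can alter who is analysed.

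**Working it through.** No sample size, power or error rate enters this point, so the check is a comparison of texts.

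| Task | 8.2 | 8.4.2 | 8.5.1 | 8.6 |
|---|---|---|---|---|
| Randomization | Pharmacist | – | – | – |
| Storage | – | Investigators and pharmacist | Pharmacy; entry for pharmacy and housekeeping staff only | – |
| Capsule or dose preparation | Pharmacist, hidden from PI and coordinator | Investigators and pharmacist | – | – |
| Dispensing and its records | – | Investigators and pharmacist (accountability) | Pharmacist | Investigators keep and verify |
| Must not know the order | Participants, PI and study team | – | – | – |

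**Step 1: dose preparation.** Sections 8.2 and 8.4.2 conflict for any investigator who belongs to the PI/study team. No section names an unblinded investigator who stands outside that team, and none divides the 8.4.2 tasks between the two parties.

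**Step 2: storage.** Section 8.4.2 includes the investigators in storage, while the access rule in 8.5.1 leaves them out. Sections 8.2 and 8.5.1 are therefore consistent with each other, and 8.4.2 is the outlier.

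**Step 3: the log.** Section 8.6 records how many units of study drug are dispensed to each participant. Two readings are open:

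- If the entry is a count of identical coded capsules, and both periods use the same number, it reveals nothing.
- If only active drug is entered, or active and placebo are entered as different items, it marks the active period. Sections 8.4.2, 8.4.3 and 8.5.1 name drug and placebo as two things, whereas 8.6 names only study drug.

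The text does not settle which reading applies. Section 8.4.1 gives the number of capsules for the placebo phase but not for the active phase, so it does not settle the matter either.

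**Step 4: extent.** Every participant receives both products, so knowledge of one period gives the other. The upper bound is 10 participants × 2 periods × 1 treatment day per period = 20 dosing days. It is reached only if investigators prepare at least one period's dose, or read an unmasked entry, for every participant.

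**Step 5: which results are exposed.** The synopsis names viral replication, immune markers and cytokines, gene expression and a TAAR1 metabolite as endpoints, all measured in the laboratory. Section 5.2 lists the incidence and nature of adverse events. Section 14 plans no between-treatment test of them. The judgement-based steps are relatedness and withdrawal.

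**The case against.** The best defence is that the specific operating text already protects the blind. The pharmacist randomizes, prepares the capsules unseen, dispenses, keeps distribution records and holds the code, and investigators have no pharmacy access. Section 8.4.2 is one general sentence. It lists reconstitution, a step described nowhere else for these capsules, which suggests carried-over wording. Its joint assignment could be carried out with the pharmacist alone doing the preparation. This lowers the chance that investigators would fill capsules. It does not remove the conflict, because no division of tasks is written and 8.4.2 is the section headed Dispensing.

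Other points on that side also have weight:

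- The hold and stop limits after the first dose in 10.4 are numeric for blood pressure and heart rate, and the solicited cardiovascular events have set grading criteria. Discretion remains for relatedness and withdrawal.
- The safety monitoring committee has access to treatment assignment (13), so its own decisions do not depend on this blind. The relatedness calls that reach it do.
- Replacement under 12.4 is automatic. The judgement lies in the withdrawal before it.
- Section 2.1 expects raised blood pressure, raised heart rate and palpitations on active drug, so staff may guess the period anyway. The bias added by 8.4.2 is therefore uncertain. A guess after dosing is still weaker than knowledge before it.

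A reader might go further and infer that the double blind is broken, that 8.2 reserves preparation to the pharmacist in so many words, that the 8.6 log necessarily reveals treatment, or that the endpoint comparison is biased. The documents do not support these readings. Section 8.2 names the pharmacist without an express exclusion, although preparing "out of sight of the study participant, study coordinator, and study site PI" has that effect for the persons listed. The content of the log is unspecified, and the endpoints are laboratory measures.

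**Conclusion.** The contradiction between 8.4.2 on one side and 8.2 and 8.5.1 on the other is plain from the text. The consequence is conditional: if 8.4.2 is followed as written, any investigator who prepares a dose knows that participant's treatment in both periods. For 8.6 the risk depends on a further condition, that the log separates active from placebo.

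The exposure falls on relatedness and withdrawal judgements. The 20 dosing days are a ceiling, and no size of bias can be derived from the documents. The conclusion assumes that the study investigators in 8.4.2 and 8.6 are part of the PI/study team in 8.2, since nothing says otherwise. The change should be made because the instruction, if obeyed, defeats the stated blinding and correcting it is easy.

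**What to change.** - **8.4.2:** state that storage, capsule preparation, individual dose preparation and active/placebo accountability are done only by the unblinded investigational pharmacist, in line with 8.2 and 8.5.1.
- **8.6:** state that the pharmacist holds the unmasked accountability record, and that the blinded team records only that a coded capsule was given, to whom and when.
- **Synopsis and 4.1:** as a consistency edit, remove the open-label description, since both places also call the study double-blind.

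The cost is protocol wording and the IRB approval that 16.1 requires for an amendment. The pharmacist already prepares the capsules under 8.2 and keeps the distribution records under 8.5.1. Sample size, visits and assays do not change.

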8.4.3 Administration Instructions

[name] and study team will instruct study staff on how to administer the study drug or placebo with a full 6 oz cup of water. Study staff will then administer the study drug or placebo and observe administration and side effects of participants on the treatment days.

8.5 Supply of Study Drug at the Site

The study drug will be purchased through procurement and delivered to the ZSFG Investigational Pharmacy located in the main Inpatient Pharmacy, Rooms 4H3 + 4H6.

8.5.1 Storage

Study drug and placebo storage will be in a cool, dry place, away from strong light, heat, or moisture. For this study, the study drug and placebo will be stored in a locked cabinet in the ZSFG Investigational Pharmacy located in the main Inpatient Pharmacy, Rooms 4H3 + 4H6. Entrance to the pharmacy is secure by electronic pass key only; limited access to pharmacy personnel and housekeeping. Temperature is controlled by air conditioning and monitored to be between 59-86 F. Temperature is recorded daily by reading an alarmed digital thermometer and recording the reading on a daily log. The CRS investigational pharmacist will dispense study drug and maintain the distribution records.

8.6 Study Drug Accountability

An accurate and current accounting of the dispensing of study drug for each participant will be maintained on an ongoing basis by the study investigators. The number of study drug dispensed will be recorded on the Investigational Drug Accountability Record. The study investigators will verify these documents throughout the course of the study.

8.7 Measures of Treatment Compliance

Study participants will be monitored in the Clinical Research Services Center (CRS) for directly observed therapy on the day(s) when study drug or placebo administered. They will be receiving clinical and laboratory assessments on those days for up to 4 hours post-treatment.

9 STUDY PROCEDURES AND GUIDELINES

Prior to conducting any study-related activities, written informed consent and the Health Insurance Portability and Accountability Act (HIPAA) authorization must be signed and dated by the participant.

A full schedule of events is shown in the Study Events Table.

Clinical Assessments

9.1.1 Concomitant Medications

All concomitant medications taken within 30 days prior to screening and entry and a complete history of ART, HIV-1 related vaccines, and immune-based therapies will be documented at the Screening and Entry visits. At each subsequent visit, all additions or discontinuations of prescription medications should be recorded. Actual or estimated start and stop dates should be recorded.

9.1.2 Demographics

Demographic information (date of birth, sex, race and ethnicity) will be recorded at Screening.

9.1.3 Medical History

At Screening, the first Baseline visit (B1) and Entry (Day 0), the medical history must include all diagnoses within the past 30 days and, regardless of when the diagnosis was made, a complete history of chronic conditions, malignancies, and AIDS-defining conditions. Self-reported or documented nadir CD4+ T cell count should be recorded. Any allergies to any medications or their formulations should also be recorded.

9.1.4 Physical Examination

A complete physical examination which includes vitals will be performed by a study physician at Screening. Targeted physical examination which includes vitals will be performed on Baseline, Study Treatment Day(s), and at Study Days 2, 31, 78, and 107..

9.1.5 Vital Signs

Body temperature, blood pressure, pulse and respirations will be performed after resting for 5 minutes at Baseline/Screening, Study Treatment Day(s), and at Study Days 2 and 31.

9.1.6 12-Lead Electrocardiogram

A 12-lead electrocardiogram (ECG) will be obtained on treatment days to evaluate for symptomatic, cardiac conduction abnormality/atrioventricular heart block that would warrant medical treatment, including: AV Block-First degree, AV Block-Second degree Mobitz Type I (Wenckebach), AV Block-Second degree Mobitz Type II, AV Block-Third degree (Complete AV block), Conduction abnormality NOS, Sick Sinus Syndrome, Stokes-Adams Syndrome, Wolff-Parkinson-White Syndrome

9.1.7 Adverse Events

Information regarding occurrence of adverse events will be captured throughout the study. Duration (start and stop dates and times), severity/grade, outcome, treatment and relation to study drug will be recorded on the case report form (CRF). Criteria for participant management, dose interruptions, modifications, and discontinuation of treatment will be mandated only for toxicities attributable to study drug.

9.2 Clinical Laboratory Measurements

9.2.1 Basic Laboratory Measures

Blood will be obtained and sent to the Zuckerberg San Francisco General Hospital clinical laboratory for complete blood count (hemoglobin, hematocrit, red blood cell count, white blood cell count, white blood cell differential, and platelet count), blood chemistry profile (serum sodium, potassium, chloride, bicarbonate, random glucose, blood urea nitrogen, creatinine), and liver enzymes (aspartate aminotransferase [AST], alanine aminotransferase [ALT], alkaline phosphatase, total bilirubin, direct bilirubin). At screening, additional laboratory measures will include Hepatitis B surface antigen and Hepatitis C antibody, thyroid panel (thyroid stimulating hormone [TSH]), and plasma β -hCG (females only).

9.3 Research Laboratory Measurements

9.3.1 HIV Clinical Laboratory Assay Measures

Blood will be obtained and sent to San Francisco General Hospital clinical laboratory for real-time determination of CD4+ and CD8+ T cell counts and plasma HIV RNA (viral load).

9.3.2 HIV Virologic Research Assay Measures

Cryopreserved PBMCs will be enriched for CD4+ T cells (StemCell, Vancouver, Canada), and DNA/RNA extracted (AllPrep Universal Kit, Qiagen, Hilden, Germany). CA-US and ms RNA will be quantified by an in-house qPCR TaqMan assay using LTR-specific primers,^{64,65} and 2-LTR DNA will be quantified using primers specific for the 2-LTR junctions.⁶⁶ Participant specimens will be assayed with up to 800 ng total cellular RNA or DNA in replicate reaction wells and copy number determined by extrapolation against a 7-point standard curve (1 – 10,000 cps) performed in triplicate.

9.3.3 Immunophenotyping

We will measure the host and viral transcriptome pre- and post-dosing by performing RNA sequencing (RNA-seq) on isolated CD4+ T-cells and applying validated bioinformatic pipelines for gene expression analysis. Transcriptomic profiling of longitudinal samples will enable characterization of the effects of oral methamphetamine on host gene expression. In addition, consideration of the gene expression data within the context of the aforementioned virologic measurements will allow us to identify specific host transcriptomic correlates of viral reactivation. We hypothesize that the expression of

particular genes (NFkB pathway components, cell-cycle regulators, cell-intrinsic immune factors) will be associated with the degree of viral reactivation.

9.3.4 Plasma cytokine measurement

Cryopreserved plasma from participants will be used to perform custom Meso Scale Discovery (Meso Scale Diagnostics, Rockland, MD) multiplex human inflammatory assays. Analytes will be assayed using an electrochemiluminescence immunoassay technique per the manufacturer's protocol and analyzed on a Meso Scale Discovery Sector Imager 2400 (MSD, Rockville, MD). TNF- α , IL 6, and IL-10 will be analyzed simultaneously in a 3-plex analysis, while TGF- β 1, TGF- β 2 and TGF- β 3 will be analyzed in a separate 3-plex cytokine analysis. The dynamic range for TNF- α , IL 6, IL-10, TGF- β 1, TGF- β 2, and TGF- β 3 per manufacturer's specifications are (in pg/mL): 0.54-3,700; 0.33-2,000; 0.14-3,700; 9.1-37,000; 2.5-38,900; and 1.4-38,600, respectively.

9.3.5 Serum and breath methamphetamine and amphetamine quantification

Amphetamine and methamphetamine concentrations in serum and breath will be determined using a clinically validated liquid-chromatography tandem mass spectrometry (LC-MS/MS) method. Sample preparation consists of acetonitrile protein precipitation, nitrogen-drying of supernatant, and reconstitution in starting LC conditions. For LC, a Shimadzu Prominence UPLC is used with a C18 column and a gradient of mobile phase A (0.05% formic acid) and B (acetonitrile/methanol). Detection is carried out with a SCIEX 4500 QTRAP® tandem mass spectrometer, with an estimated LLOD of 5 ng/mL.

9.3.6 Urine qualitative toxicology

Urine qualitative toxicology testing will be performed at baseline, screening, treatment day, and post-24 hours and post-day 31 after treatment day using a liquid chromatography high mass resolution tandem mass spectrometry (LC-HRMS) method⁶⁷ that allows for the identification of drugs and their metabolites in one assay that has enhanced sensitivity/specificity compared to traditional drug screening immunoassays using LC-MS/MS. Prior to analysis, urine samples will be extracted using matrix dilution method, respectively. The data can be retrospectively analyzed for drugs and metabolites of interest given the untargeted acquisition method, with data collected for all compounds within the mass range of 50-700 daltons. The method has been fully validated for the qualitative detection of 250 drugs and metabolites with lower limits of detection (LLOD) ranging from 0.1 – 50 ng/mL.

9.3.7 Hair ART and MA measurements

Concentrations of ART will be quantified from human hair samples at baseline only. Hair ART and MA assessment will be performed using validated liquid chromatography/ tandem mass spectrometry (LC-MS/MS) methods.⁶⁸⁻⁷⁰ Measurements from this validated assay allow quantification of protease inhibitors (PIs), non-nucleoside reverse transcriptase inhibitors (NNRTIs), and integrase strand transferase inhibitors (INSTIs) using 20-30 strands of human hair (~1-3 mg) and tenofovir (TFV) and emtricitabine (FTC) from 50-100 strands of hair (~5-10

mg). TFV measurements include tenofovir disoproxil fumarate (TDF) as well as tenofovir alafenamide (TAF).⁷¹ These methods are now being adapted in the UCSF Hair Lab to analyze MA and its metabolites, applying previously published methods,^{71,72} and costs have been included in the budget of this proposal to allow adequate ability for the development and validation of these measures

9.3.8 Trace amine receptor 1 metabolite quantification

Beta-phenethylamine (\square -PEA) concentrations in urine will be determined using a clinically validated LC-MS/MS method by [name] at the ZSFG Toxicology lab; this will include costs to perform assay development to identify additional trace amines, such as tryptamine and \square -tyramine.⁷³ LC will be performed using a Shimadzu Prominence UPLC with a C18 column. Detection will be carried out with a SCIEX 4500 QTRAP® tandem mass spectrometer.

